## 6.7.3 Food and Fluid intake

Subjects will be provided food and non-alcoholic beverages by the CTU during the dosing period of the trial. Subjects will fast at least 6 hours prior to blood draw on days of clinical laboratory testing (screening, Day -2, Day 1 [pre-dose], Day 2, Day 3 and Day 14 [ $\pm$  3 days]). Subjects will fast for at least 6 h before dosing on Day 1 and 2 h after dosing. In addition, subjects will fast from 4 hours before to at least 2 hours after bronchoscopy. A light nutritional broth or beverage may be served if bronchoscopy is scheduled 4 h to 8 h after dosing on Day 1. Water can be taken *ad lib* during those periods of fasting. Water consumption will be at least 2 L daily from the time of dosing to 48 h (Day 2) after dosing, and the time and amount consumed will be recorded.

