#### 7.5.2 DAY 2: Inpatient Follow-up – Bronchoscopy T5

For a subject assigned to lung PK timepoint group T5:

- Perform bronchoscopy with BAL on Day 2 at 24 h (± 1 h) after dosing as described for subjects in cohorts T1-T4 (see Section 7.5.1, Day 1, *After Dosing*).
  - Collect BAL samples for PK analysis once per subject at the assigned timepoint, 24 h (±1 h) (T5) after initiation of dosing, as described in Section 8.5, corresponding to the assigned cohort T5.

Note 1: Collect plasma sample for total apramycin concentration within 5 min of the corresponding BAL procedure at 24 h ( $\pm$  1 h) after initiation of the infusion. If collection of BAL samples is delayed, plasma sample will be collected at the indicated nominal timepoint (and allowable windows), and an additional plasma PK will be collected within 5 min after the last BAL sample. (See Section 8.5.1) Note 2: Urea will be measured in plasma collected at the same nominal timepoint as the plasma PK sample or in the plasma PK sample that is collected within 5 min after the last BAL sample.

- Monitor subject closely until fully recovered per bronchoscopy instructions.
  - Provide oxygenation as needed.

For all subjects:

- Obtain single 12-lead standard ECG with 10-sec rhythm strip at 24 h (±1 h) and 36 h (±1 h) after dosing.
- Obtain VS at 24 h  $(\pm 1 h)$  and 36 h  $(\pm 1 h)$  after dosing.

- Obtain blood (plasma) PK samples for total apramycin at 24 h (±1 h) and 36 h (± 1 h) after dosing.
  - An aliquot of plasma PK collected at 36 h ( $\pm$ 1 h) after starting the IMP infusion will be used in the protein binding test (for the measurement of free apramycin).
- Obtain blood and urine samples for safety clinical laboratory tests that include a calculation of GFR by the CKD-EPI equation at 24 h (±1 h) after dosing.
- Check on infusion site at 24 h ( $\pm$ 1 h) and 36 h ( $\pm$ 1 h) after dosing.
- Perform TEAE and SAE assessments.
- Perform symptom-directed (focused) PE for evaluation of TEAEs as needed.
- Document ConMeds.
- Encourage water intake at least 2 L daily Document time and volume consumed.
- Counsel to avoid rigorous physical activity and avoid caffeinated beverages.

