#### 7.5.3 DAY 3: Inpatient Follow-up

- Obtain 12-lead standard ECG with 10-sec rhythm strip at 48 h (±1 h) and 60 h (±1 h) after dosing.
- Obtain VS at 48 h ( $\pm$ 1 h) and 60 h ( $\pm$ 1 h) after dosing.
- Obtain blood (plasma) PK samples for total apramycin at 48 h (±1 h) and 60 h (±1 h) after dosing.
- Obtain blood and urine samples for clinical laboratory tests that include a calculation of GFR by the CKD-EPI equation at 48 h (±1 h) after dosing.
- Obtain blood sample for Cystatin C and urine sample for KIM-1 (exploratory biomarkers of renal injury) at 48 h (±1h) after dosing.
- Perform otoacoustic assessments.
  - Ear otoscopy.
  - Audiometry (pure tone audiometry including high frequencies).
  - DPOAEs.

Note: Day -2 otoacoustic assessments may be completed on Day 3 (+2 days) if needed.

- Check on infusion site at 48 h ( $\pm 1$  h) and 60 h ( $\pm 1$  h).
- Perform TEAE and SAE assessments.
- Document ConMeds.
- Perform complete PE.
- Counsel on use of contraception (males and females), avoidance of pregnancy (women of childbearing potential), avoidance of prohibited medication, illicit drugs, alcohol, nicotine products, vigorous exercise, and exposure to loud noises.
- Instruct on the next scheduled visit.
- Discharge subject from the CTU after review of clinical laboratory tests, ECGs and other assessments by PI or authorized clinician and audiologist.

Note 1: If the time of discharge is late in the evening, due to delays in starting procedures on Day 1 or personal reasons (such as distance from residence), the subject may stay in the CTU overnight and be discharged the following morning.

Note 2: If otoacoustic assessments could not be performed on Day 3, the subject will be discharged from the CTU on Day 3 after all other assessments are completed. Otoacoustic assessments will be completed up to Day 3 (+2 days) as outpatient.

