### Table 1: Schedule of Events

#### DMID Protoco20-0012SMIS Apramycin

Charle of influeion site					Х	v	v				v	v	v	Х	Х	Х		v	
Check of infusion site						л	л				л	л	л					Λ	
Treatment- emergent adverse events (TEAE) and serious AEs (SAEs) 					Х	Х	Х	х	х	х	х	х	Х	х	Х	Х	х	х	х
Blood (plasma) sampling for apramycin PK 				х		Х	Х	Х	Х	х	Х	Х	Х	х	Х			х	
Protein Binding Test 						Х							Х						
Administration of sedative or anesthetic medication 						Х		х	х	х		Х							
Bronchoscopy /BAL (for ELF and AM PK) 						Х		х	х	х		Х							
Oxygenation support (TBC)					х	Х	Х	х	х	х	х	Х							
Drinking schedule 					х	Х	Х	х	х	х	х	х	Х	х				Х	
Counseling 	Х	Х	Х	Х	Х	Х	Х	Х	Х	Х	Х	Х	Х	Х	Х	Х		Х	

1. Screening including Ear -Nose-Throat (ENT)/Audiology assessments are planned to be completed in a single Screening Visit. If schedule cannot be accommodated, ENT/Audiology assessments will be completed on a second visit within the screening period.

2. Inclusion and exclusion criteria regarding ENT/Audiology assessments to be reviewed by audiologist.

- 3. Review of inclusion and exclusion criteria on Day -2 to determine eligibility for admission; on Day -1, before 12-lead ECG, to determine eligibility for enrollment; and on Day 1 pre-dose to confirm the subject remains eligible for dosing.
- 4. Medical history update to include pre-dose events.
- 5. Vital signs include systolic and diastolic BP, heart rate, respiratory rate and oral temperature.
- 6. 12-lead ECG single recording with 10 sec rhythm strip.
- 12-lead ECG: triplicate safety ECGs with 10 sec rhythm strips on Day -1 at the same timepoints as the projected timepoints for ECGs to be recorded on Day 1, and on Day 1 within 30 min of dosing, and at 1h (± 5 min), 4h (± 10 min) and 16 h (± 15 min) after starting the apramycin dose. Record ECG before VS and PK draws and, at 4 h post-dosing, before administration of sedation or anesthetic for BAL in cohort T3.
- 8. Hepatitis B surface antigen (HBsAg), hepatitis virus C antibody (HCV) and human immunodeficiency virus (HIV) antibody.
- 9. Clinical laboratory tests under fasting conditions: hematology, coagulation, and clinical chemistry panels and thyroid stimulating hormone (TSH) & free T3/free T4. (See Section 8.2.1)

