- 20. Blood samples for plasma PK are taken pre-dose, and at 30 (± 5) minutes (end of infusion) and 1 h (±5 min), 2 h (±5 min), 4 h (±10 min), 8 h (±15 min), 16 h (±15 min), 24 h (±1 h), 36 h (±1 h), 48 h (±1 h) and 60 h (±1 h) after start of the infusion Blood samples for plasma PK are taken at the nominal timepoints. If collection of BAL is delayed, plasma PK will be collected at the nominal timepoint and again within 5 min after collection of the last BAL sample. In that case, total apramycin concentration will be measured in both samples, but only the drug concentration in the delayed plasma PK sample will be used to calculate the Lung PK/Plasma PK ratio.
- 21. A protein binding test for the measurement of free apramycin will be performed using aliquots of plasma PK samples collected at 0.5 h (± 5 min) and 36 h (± 1 h) after start of infusion.
- 22. Type of sedation or light anesthesia medication for bronchoscopy/BAL procedure and local anesthetic TBD by the anesthesia and bronchoscopy protocols.
- 23. Each subject is assigned to a single bronchoscopy/BAL procedure. Lung PK samples (for measurement of total apramycin concentration) after initiation of infusion and corresponding cohorts (T) are: (Cohort T1), 30 min (±5 min); (Cohort T2), 2 h (±5 min); (Cohort T3), 4 h (±10 min); (Cohort T4), 8h (±15 min); and (Cohort T5), 24 h (±1 h). Lung PK timepoints are aligned with plasma PK samples collected for the measurement of total apramycin concentration at 30 min (±5 min), 2 h (±5 min), 4 h (±10 min), 8 h (±15 min) and 24 h (±1 h) after start of apramycin infusion, If BAL is delayed, plasma sample will be collected at the nominal timepoint and again within 5 minutes after the last BAL sample collection. Urea will be measured at the same timepoints in plasma and BAL (ELF) samples.
- 24. Subjects to be kept hydrated water starting 30 min before until 24 h after start of infusion (document time and volume of water intake).
- 25. Provide counseling at the end of each encounter with the subject. Counsel on use of contraception (males and females), avoidance of pregnancy (women of childbearing potential), avoidance of sperm donation, and avoidance of prohibited medications, illicit drugs, alcohol, nicotine products, vigorous exercise, and exposure to loud noises.

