. Each participant is assigned to a single bronchoscopy/BAL procedure. Lung PK samples (for measurement of total apramycin concentration) after initiation of infusion and corresponding cohorts (T) are: (Cohort T1), 30 min ( $\pm 5$  min); (Cohort T2), 2 h ( $\pm 5$  min); (Cohort T3), 4 h ( $\pm 10$  min); (Cohort T4), 8h ( $\pm 15$  min); and (Cohort T5), 24 h ( $\pm 1$  h). Lung PK timepoints are aligned with plasma PK samples for measurement of total and free apramycin concentration at 30 min ( $\pm 5$  min), 2 h ( $\pm 5$  min), 4 h ( $\pm 10$  min), 8 h ( $\pm 15$  min) and 24 h ( $\pm 1$  h) after start of apramycin infusion. If BAL is delayed, plasma sample will be collected at the nominal timepoint and again within 5 minutes after the last BAL sample collection. Urea will be measured at the same timepoints in plasma and BAL (ELF) samples.  Participants to be kept hydrated water starting 30 min before until 24 h after start of infusion (document time and volume of water intake).

. Provide counseling at the end of each encounter with the participant. Counsel on use of contraception (males and females), avoidance of pregnancy (women of childbearing potential), avoidance of sperm donation, and avoidance of prohibited medications, illicit drugs, alcohol, nicotine products, vigorous exercise, and exposure to loud noises.

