### 14.3.5.5 Kidney Function Biomarker Results

# Table 49:Kidney Function Biomarker Summary Statistics Measurement and Change from
Baseline by Parameter and Timepoint – Safety Population

				Measu	urement			Change fr	om Baselin	e
Parameter	Timepoint	Ν	Mean	SD	Median	Min, Max	Mean	SD	Median	Min, Max
Serum Cystatin C (mg/L)	Baseline	X	XX.XX	XX.XX	XX.XX	xx.x, xx.x	-	-	-	-
	Day 3, 48 h Post-Dose	х	xx.xx	xx.xx	xx.xx	xx.x, xx.x	xx.xx	XX.XX	XX.XX	xx.x, xx.x
	Day 14	х	xx.xx	xx.xx	xx.xx	xx.x, xx.x	XX.XX	XX.XX	XX.XX	xx.x, xx.x
	Day 30	х	xx.xx	XX.XX	xx.xx	xx.x, xx.x	XX.XX	XX.XX	XX.XX	xx.x, xx.x
Urinary KIM-1 (ng/mL)	Baseline	Х	XX.XX	XX.XX	xx.xx	xx.x, xx.x	-	-	-	-
	Day 3, 48 h Post-Dose	х	xx.xx	xx.xx	xx.xx	xx.x, xx.x	xx.xx	xx.xx	XX.XX	xx.x, xx.x
		х	xx.xx	xx.xx	xx.xx	xx.x, xx.x	XX.XX	xx.xx	XX.XX	xx.x, xx.x
Urinary KIM-1 Normalized (ng/mg creatinine)	Baseline	х	XX.XX	xx.xx	xx.xx	xx.x, xx.x	-	-	-	-
		х	xx.xx	XX.XX	xx.xx	xx.x, xx.x	xx.xx	XX.XX	XX.XX	xx.x, xx.x
Notes: N = Number recent measurement	of participants in the Safe prior to start of infusion.	ety Popu	ulation with	n the labora	tory result	assessed at th	e respectiv	ve timepoint	. Baseline =	The most

Table with similar format:

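### The hydration instruction ends at 24 h in the Table 1 footnote but at 48 h in Section 6.7.3 and in the footnoted row itself, and the disputed day leads into the 48-h renal samples

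*Protocol*

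**What the plan says.** The instruction on water intake appears in these places:

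- **Protocol Table 1, footnote 24:** "Subjects to be kept hydrated water starting 30 min before until 24 h after start of infusion", with time and volume of intake to be documented.
- **SAP Table 2, footnote 24:** "Participants to be kept hydrated water starting 30 min before until 24 h after start of infusion".
- **Protocol Table 1, row "Drinking schedule":** marked at 0, 0.5, 1, 2, 4, 8, 16, 24, 36 and 48 h and at early termination. There is no mark at pre-dose or at 60 h. The same row in SAP Table 2 has the same marks.
- **Protocol Section 6.7.3:** "Water consumption will be at least 2 L daily from the time of dosing to 48 h (Day 2) after dosing", with time and amount recorded.
- **Protocol Sections 7.5.1 and 7.5.2 (Days 1 and 2):** "Encourage water intake at least 2 L daily Document time and volume consumed".
- **Protocol Section 7.5.3 (Day 3):** no instruction on water intake or on recording it. This list opens the 48-h assessments, including the "urine sample for KIM-1 (exploratory biomarkers of renal injury) at 48 h (±1h) after dosing".
- **Protocol Sections 7.3 and 7.4 (Days -2 and -1):** good hydration is encouraged, with no volume target.

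**The concern.** The kidney is the main target organ in the repeat-dose toxicity studies summarised in protocol Section 2.2. The 48-h visit carries chemistry with creatinine, BUN and eGFR, urinalysis, and the first cystatin C and KIM-1 samples after dosing.

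Under footnote 24, that visit follows a day with no hydration rule and no duty to record intake. Under Section 6.7.3, it closes two days with a daily minimum of 2 L, both recorded. An operating instruction in a renal-safety setting should not depend on which page is open. If the recording stops at different times in different participants, the intake record cannot be used afterwards to judge the 48-h urine and serum values.

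**Working it through.** No sample size, power or error rate depends on this point, and the plan gives no figure to reproduce. The check is a comparison of the passages, plus two short pieces of arithmetic.

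**1. Start, end and recording**

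| Place | Start | End | Intake recorded |
|---|---|---|---|
| Footnote 24 (protocol, SAP) | 30 min before infusion | 24 h | yes, within this interval |
| Table 1 row | 0 h (no pre-dose mark) | 48 h | by reference to the footnote |
| Section 6.7.3 | dosing | 48 h, labelled Day 2 | yes |
| Sections 7.5.1 and 7.5.2 | Day 1, after dosing | Day 2 | yes |
| Section 7.5.3 | none | none | none |

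The numeric end times are 24 h and 48 h. Footnote 24 disagrees with its own row and with Section 6.7.3. The start differs between the footnote and both of the others. The SAP footnote matches the current protocol footnote, so the conflict is not a difference between the two documents.

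**2. Day label.** Dosing is on Day 1 and there is no Day 0 (SAP Section 3.3.4). Taking Day = 1 + whole 24-h periods since dosing:

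- 24 h: 1 + 1 = Day 2
- 36 h: 1 + 1 = Day 2
- 48 h: 1 + 2 = Day 3
- 60 h: 1 + 2 = Day 3

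This agrees with Sections 7.5.2 and 7.5.3. The Day 2 label in Section 6.7.3 is therefore wrong for 48 h.

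**3. Size of the disputed period.** 48 h − 24 h = 24 h. At the daily minimum in Section 6.7.3, two days require at least 2 × 2 L = 4 L. The disputed day accounts for at least 2 L of that, which is half. Footnote 24 sets no volume at all.

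**4. What sits at the boundary.** Cystatin C and KIM-1 are sampled on Day -2, pre-dose on Day 1, at 48 h, on Day 14 and on Day 30 (Sections 8.2.8.1 and 8.2.8.2), so 48 h is the first post-dose value. Creatinine, BUN, eGFR and urinalysis are also taken at 24 h, a time that lies within the hydration period under every passage.

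**5. KIM-1 and dilution, a separate matter.** Let E be the amount of KIM-1 excreted per day, C the amount of creatinine and V the urine volume.

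- Raw concentration = E/V. With E constant, change from baseline = V0/V1 − 1.
- Normalised value = (E/V)/(C/V) = E/C, which does not involve V.

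The documents give no urine volumes. Assumed values serve only to show that the direction is open: 1.5 to 2.0 L/day gives 1.5/2.0 − 1 = −25%, and 2.0 to 1.5 L/day gives 2.0/1.5 − 1 = +33%. The normalised form changes by 0% in both cases.

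**The case against.** The strongest reply is that most passages can be read together. The Table 1 row, Section 6.7.3 and the Day 1 and Day 2 visit lists all fit roughly two days from dosing, and the silence on Day 3 is then what one would expect. On that view, one footnote and its SAP copy are out of line, and there is one slip in a day label. The observation about the pattern stands. It does not say which passage governs, and footnote 24 is the text attached to the row that staff use at the bedside.

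It can also be said that KIM-1 and cystatin C are exploratory, that all analyses are descriptive, and that these markers are neither named in the halting criteria nor listed among the interim SMC data in SAP Section 6.6. This is correct and limits the consequence for the trial's conclusions. The 48-h visit also carries ordinary graded safety laboratory tests, however, so the timepoint is not purely exploratory.

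Three stronger readings are tempting, and the documents do not support them.

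- **Three end times.** A reader might count footnote, section and table separately. The table row and Section 6.7.3 both end at 48 h. A third reading, the end of Day 2, arises only if the wrong day label is allowed to override the hour.
- **The schedule conflict produces a dilution effect in raw KIM-1.** It does not follow. Raw concentration depends on urine volume at 48 h relative to baseline, and the baseline has no volume target. Aligning every passage to either end time would leave that contrast in place.
- **A hidden injury signal of a given size.** Any percentage rests on assumed urine volumes, and the direction can go either way. The SAP already tabulates and plots KIM-1 per mg urinary creatinine (Section 9.6.1, Tables 49 and 50, Figures 75 and 76), which removes simple dilution.

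**Conclusion.** The contradiction is real: end times of 24 h and 48 h, two different starts, and 48 h assigned to the wrong day. It covers 24 h of fluid intake and its recording, immediately before the 48-h renal samples. It should be corrected because it changes what staff do and record, which makes it more than a typing error.

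Its consequence for the analysis is limited and cannot be quantified from the documents. No primary or secondary result is shown to be biased, and normalised KIM-1 is already planned. The one open analytical question is small: the exploratory endpoint is worded as a KIM-1 concentration, both raw and normalised forms are summarised, and neither document says which one is to be interpreted. The dilution argument assumes constant excretion of KIM-1 and creatinine. No view is taken here on which hydration period is right.

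**What to change.** Reconcile the hydration and intake-recording period to one start, one end and one day label in protocol Sections 6.7.3 and 7.5.1 to 7.5.3, in the Table 1 row and footnote 24, and in the SAP Table 2 row and footnote. State the interval in hours from the start of infusion and make its relation to the 48-h samples explicit. The choice of interval is the sponsor's clinical decision.

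As an optional clarification, add a sentence to SAP Section 9.6.1 saying that change from baseline is interpreted on KIM-1 per mg urinary creatinine, with the raw concentration as supportive.

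The cost is wording in the protocol, its schedule and the SAP. No sample, visit or assay is added, and the normalised KIM-1 displays already exist.

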## **Appendix B: Adverse Events Toxicity Grading Criteria**

#### ABBREVIATIONS: Abbreviations utilized in the Tables:

- ADL = Activities of Daily Living
- CTU = Clinical Trial Unit
- ULN = Upper Limit of Normal
- IV = Intravenous

#### **ESTIMATING SEVERITY GRADE**

For abnormalities NOT found elsewhere in the Toxicity Tables, use the scale below to estimate grade of severity:

GRADE 1	Mild	Events require minimal or no treatment; do not interfere with the subject's daily activities.
GRADE 2	Moderate	Events result in a low level of inconvenience or concern with therapeutic measures; may cause some interference with functioning.
GRADE 3	Severe	Events interrupt a subject's usual daily activity and may require systemic drug therapy or other treatment; are usually incapacitating.

#### SERIOUS OR LIFE-THREATENING AEs

Clinical events considered to be serious or life-threatening include, but are not limited to seizures, coma, tetany, diabetic ketoacidosis, disseminated intravascular coagulation, diffuse petechiae, paralysis, acute psychosis, and severe depression.

#### **COMMENTS REGARDING THE USE OF THESE TABLES**

- Standardized and commonly used toxicity tables (Division of AIDS, National Cancer Institute [NCI] Common Toxicity Criteria [CTC], and World Health Organization [WHO]) have been adapted for use by the Division of Microbiology and Infectious Diseases (DMID) and modified to better meet the needs of subjects in DMID trials.
- For parameters not included in the following Toxicity Tables, the CTU will refer to the "Guide for Estimating Severity Grade" located above.
- Criteria are generally grouped by body system.

Some protocols may have additional protocol specific grading criteria, which will supersede the use of these tables for specified criteria.

Clinical AEs	Reference range	Mild (Grade 1)	Moderate (Grade 2)	Severe (Grade 3)
VITAL SIGNS 				
Fever - °C	36.1 - 37.2 	37.3 - 38.4	38.5 - 38.9	>38.9
Fever - °F	97.0 - 99.0 	99.1 - 101.1	101.2 - 102.0	>102.0
Tachycardia - bpm	50 - 100 	101 - 115	116 - 130	>130 or ventricular dysrhythmias
Bradycardia – bpm		45 - 49	40 - 44	<40
Hypertension (systolic) - mmHg	130/89 2,3,4,5	131 - 150	151 - 160	>160
Hypertension (diastolic) - mmHg		90 - 95	96 - 100	>100
Hypotension (systolic) - mmHg		85 - 88	80 - 84	<80
Tachypnea – breaths per min	10 - 20 	21 - 25	26 - 30	>30

#### Table 2: Toxicity Grading Tables – CLINICAL AEs

Note 1: No recent hot or cold beverages or smoking. A protocol should select either C or F for inclusion

Note 2: Assume awake and in supine position for 5 min at rest. For TEAE, measurements at least 3 times with 2 concordant results (See Section 8.1.6)

Note 3: Abnormal HR and BP on first measurement may be repeated twice more with the subject resting between measurements for at least 5 min (See Section 8.1.6).

*Note 4*: Exceptions to screening BP and HR reference range are:

- (a) Subjects with baseline  $HR \ge 45$  to 50 bpm may be accepted if they do not have symptomatic bradycardia, including syncope, heart disease, ECG abnormalities, or history of syncope or use of medication
- (b) Subjects with baseline SBP up to 140 mmHg and DBP up to 90 mmHg may be accepted if they do not have MH of symptomatic hypertension, including paroxysmal hypertension, heart disease, renal disease, CNS disease, visual abnormalities or evidence of peripheral vascular disease, ECG abnormalities, use of medication, use of illicit drugs or FH of hypertension
- Note 5: Isolated/individual abnormalities of VS would not be considered toward halting criteria. Abnormalities of VS will be described as "increased X" or "decreased X" (X = HR, BP, RR, temperature) if asymptomatic, transient and not associated with a systemic or organ-specific disorder and coded by MedDRA within the System Organ Class (SOC) "Investigations." These abnormalities will be graded per criteria in this table, but not considered in determining whether study stopping criteria have been met. On the other hand, abnormalities of VS that are either secondary to systemic or organ-specific clinical syndrome or primary disorders will be coded in the appropriate SOC (e.g., "cardiac disorders", "respiratory disorders", "immunological disorders", etc). These abnormalities will be considered in determining whether stopping criteria have been met.

Clinical AEs	Mild (Grade 1)	Moderate	Severe (Grade 3)					
CARDIOVASCULAR		(01auc 2)	(Grade 5)					
Arrhythmia		Asymptomatic or transient signs; no medical intervention required.	Recurrent and/or persistent signs; symptomatic medical intervention required.					
Hemorrhage	Estimated blood loss ≤100 mL.	Estimated blood loss >100mL; no transfusion required.	Blood transfusion required.					
RESPIRATORY								
Cough	Transient cough no treatment required.	Persistent cough treatment required.	Interferes with daily activities.					
Bronchospasm, Acute	Transient bronchospasm no treatment required; FEV1 71- 80% of predicted peak flow.	Requires treatment; normalizes with bronchodilator; FEV1 60- 70% of predicted peak flow.	No normalization with bronchodilator; FEV1 <60% of predicted peak flow.					
Dyspnea	Does not interfere with usual and social activities.	Interferes with usual and social activities; no treatment.	Prevents usual and social activities OR requires treatment.					
EAR AND LABYRIN	TH DISORDERS							
Hearing Impairment (Adult enrolled on a Monitoring Program (on a 1, 2, 4, 3, 6, and 8 kHz audiogram)	Threshold shift of 15 - 25 dB averaged at 2 contiguous test frequencies in at least one ear.	Threshold shift of >25 dB averaged at 2 contiguous test frequencies in at least one ear.	Threshold shift of >25 dB averaged at 3 contiguous test frequencies in at least one ear; therapeutic intervention indicated.					
Tinnitus	Mild symptoms intervention not indicated.	Moderate symptoms; limiting instrumental ADL.	Severe symptoms; limiting self-care ADL.					
Vertigo	Mild symptoms.	Moderate symptoms; limiting instrumental ADL.	Severe symptoms; limiting self-care ADL.					
GASTROINTESTINA	AL							
Nausea	No interference with normal activity.	Some interference with normal activity.	Prevents daily activities.					
Vomiting	No interference with activity OR 1-2 episodes in a 24-h period.	Some interference with activity OR >2 episodes in a 24-h period.	Prevents daily activity OR requires medical intervention.					

